6.2.4.3. Sensitivity Analyses

Based on FDA correspondence related to written feedback for Arctic Front family of cryoballoon catheters; Freezor Max cardiac cryoablation catheter (Q181709/S001; received by Medtronic January 18, 2019), sensitivity analyses will be performed to assess the possible effects of missing AFEQT and SF-12 scores upon the hypotheses that are tested. For both outcomes, sensitivity analyses will investigate a "worst-case" scenario, in which missing responses for questions at baseline are assumed to be from the highest possible level (leading to the highest possible group average score at baseline). Missing responses to survey questions at 6-month and 12-month visits are assumed to be values indicating the lowest levels of mental and physical QoL. Hypothesis testing will proceed for the AFEQT using the same methods outlined in section 6.2.4.1, and will use the methods outlined in section 6.2.4.2 for the SF-12. If the statistical significance does not differ between the worst-case and complete case analyses, it will be concluded that the findings are robust to missing data. Meanwhile, if the worst-case scenario from the observed complete-cases scenario differs in terms of statistical significance, the sensitivity will be noted, and further investigation may occur while utilizing less extreme assumptions about missing data patterns.

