6.2.4.1. AFEQT

The AFEQT questionnaire will be utilized for this objective. The questionnaire is an atrial fibrillation specific health-related quality of life questionnaire to assess the impact of AF on a subject's life. The overall score ranges from 0 – 100, with 0 corresponds to complete disability and 100 corresponds to no disability.

Hypothesis

The following hypothesis will be tested in a one-sided test at the 0.025 significance level:

$$H_0: \Delta AFEQT = 0$$

$$H_a: \Delta AFEQT > 0$$

Where $\Delta AFEQT$ is the change in AFEQT score from baseline to 12 months.

Analysis Methods

Change in AFEQT score is defined as 12-month AFEQT score minus baseline AFEQT score. Change in AFEQT scores will be assessed utilizing a one-sample t-test. A two-sided 95% confidence interval will be calculated based on the t-distribution.

Additionally, summary statistics (e.g. mean, SD, median, range) and graphical methods will be used to summarize the change in AFEQT scores from baseline through 12 months. The outcome variable for this objective requires both a baseline and a follow-up assessment of AFEQT scores with answers for all questions. Analysis will be performed on the mITT dataset for those subjects that have completed at least 50% of the questions for each subscale at baseline and 12-months.

Performance criteria

If the p-value from the one-sample t-test after adjusting for the Hommel procedure is < 0.025 , the objective will be considered met.

Additional Analyses

The AFEQT questionnaire has three subscale scores, Daily Activities Subscale, Treatment Concern, and Treatment satisfaction. Each subscale ranges from 0 – 100, where 0 corresponds to low quality-of-life and 100 corresponds to high quality of life.

Change in AFEQT subscale score is defined as 12-month AFEQT subscale score minus baseline AFEQT subscale score. A two-sided 95% confidence interval will be calculated based on the t-distribution.

² Hommel, G. A stagewise rejective multiple test procedure based on a modified Bonferroni test. *Biometrika* 1988; 75, 383-386.

answered. Analysis will be performed on complete cases within the mITT dataset, in subjects that have completed both a baseline and 12-month questionnaire.

Performance criteria

If the p-value from the one-sample t-test after adjusting for the Hommel procedure is < 0.025 , the objective will be considered met.

Additional Analyses

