6.5. Adjustments for Multiple Comparisons

A Hommel multiple testing procedure will be utilized to maintain an overall type I error rate of 0.025 for the three hypotheses tested as part of the secondary objective³. Testing for this objective will be performed if the primary objectives are met. The Hommel procedure is a "step-up" method of error adjustment.

The three hypotheses associated with the secondary objective (see 6.2.3) will be denoted here as H(1), H(2), and H(3). H(1), H(2) and H(3) denote the null hypothesis for change in AFEQT, change in SF-12 mental component, and SF-12 physical component. For each of the hypotheses, p-values will be calculated and sorted $p(1) < p(2) < p(3)$. The decision rule to accept or reject each hypothesis will follow the step-up algorithm, where $\alpha=0.025$.

Step 1: If $p(3) > \alpha$, accept H(3) and go to Step 2, otherwise reject all hypotheses and stop

Step 2: If $p(2) > \alpha/2$, accept H(2) and go to Step 3, otherwise reject all remaining hypotheses and stop

Step 3: If (1) $\alpha/2 < p(2) \leq 2\alpha/3$ and $p(1) \leq \alpha/2$ or (2) $p(1) \leq \alpha/3$, reject H(1); otherwise accept H(1).

³ Hommel, G. A stagewise rejective multiple test procedure based on a modified Bonferroni test. *Biometrika* 1988; 75, 383-386.

Demographic strata with <5 events will be combined with other strata if the resulting combination is still deemed analytically meaningful, or may be ignored due to information sparsity. Age will be calculated as [year of baseline date – year of birth] as the case report form does not collect the exact date of birth for a subject. For subgroup analysis, age will be divided into quartiles. The log-rank test will be utilized. If the overall log-rank test of equality over strata is significant for strata with more than two levels, Tukey's range test will be used to adjust type I error for the comparison between multiple subgroups. Subgroup analyses will be performed in the same datasets in which the corresponding primary or secondary objectives are analyzed.

In addition to subgroup analyses by demographic variables, there are eight pre-specified subgroup analyses that will be performed:

- by Left Atrial Diameter (LAD) at the most recent measurement prior to the procedure;
- by duration of persistent AF, measured in terms of months prior to the procedure;
- by number of prior failed AAD's
- by history of hypertension (binary)
- by history of cardioversion (binary)

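### The quality-of-life robustness rule in SAP 6.2.4.3 works in one direction only: at the planned 10% attrition, a non-significant AFEQT or SF-12 result will in practice always be called robust to missing data

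*SAP*

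**What the plan says.** For AFEQT, SAP 6.2.4.1 states: "The following hypothesis will be tested in a one-sided test at the 0.025 significance level". The alternative is a positive change from baseline to 12 months. The method is equally plain: "Change in AFEQT scores will be assessed utilizing a one-sample t-test". On the overall score, "0 corresponds to complete disability and 100 corresponds to no disability", so higher is better. SAP 6.5 adds the two SF-12 component scores and the multiplicity control: "A Hommel multiple testing procedure will be utilized to maintain an overall type I error rate of 0.025" for the three hypotheses. It also sets a gate: "Testing for this objective will be performed if the primary objectives are met".

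The missing-data check is in SAP 6.2.4.3. At baseline, "missing responses for questions at baseline are assumed to be from the highest possible level". At follow-up, "Missing responses to survey questions at 6-month and 12-month visits are assumed to be values indicating the lowest levels of mental and physical QoL". The same tests are then repeated, and the verdict follows from comparing significance status: "If the statistical significance does not differ between the worst-case and complete case analyses, it will be concluded that the findings are robust". If the status differs, the sensitivity is noted and milder assumptions may be tried. If it agrees, no further step is planned. The tipping-point analysis in SAP 6.4 covers the two primary endpoints, not quality of life.

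**The concern.** The worst case is a sound challenge to a positive finding: if improvement survives it, missing data did not create the improvement. It is no challenge to a negative finding, because it moves the estimate further in the direction already found. For a hypothesis that is not rejected, the open question is whether missing data hid an improvement, and the planned scenario does not address that.

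The rule nevertheless treats agreement as evidence of robustness in both situations. For a non-rejected hypothesis, the missing-data conclusion would come from the rule and not from the data. The three hypotheses are judged separately under Hommel, so one could be rejected and another not, and the second would then carry an unsupported statement in the study report.

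**Working it through.** **Inputs from the documents.** One-sided alpha is 0.025, with Hommel over three hypotheses (SAP 6.2.4.1, 6.5). Attrition is 10% (SAP 6.4, 7.1). The SAP's own figure reproduces: 150 × (1 − 0.1) = 135 analysed, so 15 are missing.

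**Assumptions.** The documents give no SD, effect size or item-missing rate for quality of life. The illustration assumes an SD of change of 9 and a worst-case fill of −25 on an SF-12 component. It also assumes that the 15 lost subjects have no 12-month questionnaire.

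**Step 1. Can filling wholly missing forms create significance?** Let S be the sum and Q the sum of squares of n changes, and r = S/√(nQ). Then t = √(n−1) · r/√(1−r²). On the 0–100 AFEQT score, a missing 12-month form is filled at the floor, so the filled change is zero or negative. Adding it does not raise S, does not lower Q, and raises n. The most favourable addition is a zero, which increases t only when |t| < 1 and then leaves it below 1. A grid check started from samples exactly at the critical value, with n from 5 to 165, 1 to 40 zeros added, and thresholds α, 2α/3, α/2 and α/3. Significance was created in 0 of 25,760 cases.

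**Step 2. Illustration.** For two groups combined, SS = (n₁−1)s₁² + (n₂−1)s₂² + [n₁n₂/(n₁+n₂)](m₁−m₂)². With 135 and 15, the bracket is 13.5.

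- Complete cases, mean +1.2: t = 1.2/(9/√135) = 1.549, p = 0.062.
- Worst case, 15 at −25: mean = (162 − 375)/150 = −1.42. SS = 10,854 + 13.5 × 26.2² = 20,121, so SD = 11.62, t = −1.50 and p = 0.93. Both analyses are non-significant, so the rule returns *robust*.
- The same 15 with mean +5, SD 9: mean = (162 + 75)/150 = 1.58. SS = 10,854 + 1,134 + 13.5 × 3.8² = 12,183, so SD = 9.04, t = 2.14 and p = 0.017.

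By the same formula, with SD 9 in the missing group, the mean gain needed among the 15 is about 3.7 points for p = 0.025, 6.0 for p = 0.0125 (α/2) and 7.3 for p = 0.0083 (α/3).

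**Step 3. AFEQT scale.** Assumptions: SD 15–25, baseline mean 40–60, again 135 observed and 15 missing. Complete-case p-values of 0.160, 0.068 and 0.030 became worst-case p-values between 0.56 and 0.99. All would be labelled robust.

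**Step 4. Partly answered forms.** The SAP fills single answers, so a subject with a few blanks can enter the worst case with a positive change. This adds evidence of improvement if that subject was outside the complete-case set. Example: 110 complete cases with mean 3 and SD 20 give p = 0.059. Adding 25 partial responders with worst-case mean 7 gives an overall mean of (330 + 175)/135 = 3.74 and p = 0.010–0.020 for an added-group SD of 10–25. Adding 15 wholly missing subjects at −50 as well (added-group SD 15) gives p = 0.79.

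An item-level simulation required all questions for a complete case and assumed a true change of 5, SD 20 and 0.5% of items missing. The table shows non-significant results that became significant.

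| Whole-form loss | 12 items | 20 items |
|---|---|---|
| 10% | 0 of 1,957 | 0 of 1,984 |
| 5% | 1 of 1,734 | 6 of 1,793 |
| 2% | 15 of 1,693 (0.9%) | 50 of 1,780 (2.8%) |
| 0% | 158 of 1,611 (10%) | 294 of 1,664 (18%) |

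**The case against.** A reader might infer that the worst case can never create significance, whichever subjects are included. The documents do not support that. Filling is by item, and SAP 6.2.4.1 describes the AFEQT set in two ways: all questions answered, and at least half of each subscale answered. For SF-12 the SAP uses complete cases. If partial responders are left out of the comparison set but enter the worst case, and few whole forms are lost, significance can appear, as Step 4 shows. The SF-12 scoring is also not in the documents, so it cannot be confirmed that every filled answer lowers both component scores. The proof in Step 1 is firm for wholly missing forms on the AFEQT score.

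The reversal should not be oversold either. A p of 0.017 is below the unadjusted 0.025 but not below 0.0125, so Hommel rejection depends on the other two p-values. A mean gain of 5 is about four times the observed 1.2.

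Finally, the worst case guards against a false claim of benefit, which is the main regulatory risk, and it was added on FDA feedback. The SAP also foresees an optional repeated-measures analysis of all available SF-12 data. These points stand and limit the consequence. They do not justify the wording of the rule: the optional analysis does not alter the stated verdict, and the partial-responder route tests no favourable assumption about missing data.

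**Conclusion.** The concern holds as a statement about practice at the planned attrition, not as an absolute. With about 15 of 150 subjects wholly missing at 12 months, agreement between the two analyses is effectively guaranteed for a non-significant result, and the label *robust* carries no information. In the illustration a result so labelled (p = 0.062, worst case 0.93) would reach p = 0.017 if the missing subjects gained 5 points on average. That rests on the assumed SD of 9 and fill of −25.

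The reach is narrow. It affects only the missing-data conclusion for a non-rejected secondary hypothesis, tested after both primary objectives are met. It cannot create a positive quality-of-life claim or change study success. It is worth correcting because the rule as written would put an unsupported statement in the report and the correction is nearly free.

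**What to change.** In SAP 6.2.4.3:

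1. Limit the worst-case robustness conclusion to hypotheses rejected in the complete-case analysis.
2. For a hypothesis not rejected, draw no robustness conclusion from the worst case. Report instead a tipping point: the mean change in the missing subjects needed to reach Hommel-adjusted significance, with the assumed spread stated.
3. State one complete-case definition for each questionnaire, resolve the two AFEQT descriptions in 6.2.4.1, and use that definition in both analyses.

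A full mirror-image best case is not a good substitute for item 2. With 135 observed at mean 0 and SD 9, filling 15 subjects at +25 gives a mean of 375/150 = 2.5 and p = 0.004. Nearly every null would then be called undetermined, again by construction.

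The cost is a few sentences and a little more programming. The downside is that some null results will no longer be called robust.

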6.2.5. Ancillary Objectives

Ancillary objectives been defined to provide additional information about the performance of the Arctic Front Advance Cardiac CryoAblation Catheter. For these objectives, no hypotheses are defined for regulatory or labeling purposes.

[Redacted]

[Redacted]

[Redacted]

- [Redacted]
- [Redacted]

[Redacted]

[Redacted]

[Redacted]

[Redacted]

[Redacted]

[Redacted]

[Redacted]

STOP Persistent AF Statistical Analysis Plan

08-JUL-2019

Version 4.0

Page 16 of 25

[Redacted text block]

[REDACTED]

6.3. Center Pooling

The STOP Persistent AF study is expected to be conducted at up to 25 study centers in the US, Canada, Europe and Japan, with a total enrollment of 225 subjects across all study centers to ensure that at least 150 are treated with the Arctic Front Advance Cardiac CryoAblation Catheter. Per the CIP, each site will treat between 0 and 15 subjects. The protocol also specifies that a combined total of no more than 45 subjects will be enrolled at Canadian Centers. The target total enrollment for all Japanese centers combined is 15 subjects.

Evidence for this study will be used in submissions to two separate regulatory bodies. The submission for indication change to the Japan Pharmaceuticals and Medical Devices Agency (PMDA) will include analysis based on subjects from all available geographies (US, Canada, and Japan), and is referred to as the PMDA cohort in this document. Meanwhile, the Pre-Market Approval Supplement (PMA-S) to the US Food and Drug Administration (FDA) will include data from subjects treated in the US, and Canada; these subjects are referred to as the "PMA-S" cohort in this SAP. For both PMA-S and PMDA cohorts, it will be assessed whether site-to-site and geographical heterogeneity exists in the rate of pre-specified primary endpoints using a random-effects meta-analytic approach. The R statistical software platform will be used to evaluate whether sites exhibit significant heterogeneity in event rates, and whether geography (a three-level categorical variable representing whether a site is located in the US, Canada, or Japan) moderates any statistically significant heterogeneity that is observed. Models will be fit separately for each primary outcome. Testing will not be performed for outcomes or strata in which heterogeneity cannot be assessed in a meaningful way (for example, if < 5 events are observed in all subjects). If a Cochran's Q-test for heterogeneity shows $p < 0.05$, it will be taken as evidence of significant heterogeneity between sites. Evidence of between-site heterogeneity will not preclude pooling data; rather, it will prompt further investigation into the sources of the apparent differences in event rates between sites. At a minimum, findings of analyses on heterogeneity between study sites and between all US, Canadian and Japanese study centers will be shown in the final report in a table by endpoint. Heterogeneity analysis findings will not change the composition of the PMA-S and PMDA cohorts as defined above. Analysis of heterogeneity will be performed within the mITT dataset, like the primary safety and efficacy analyses are.

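### The only geography test visible in SAP 6.3 is worded as conditional on a significant site-level Q, which would hide most large US-Canada differences

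*SAP*

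**What the plan says.** SAP 6.3 (Center Pooling) states its aim for both the PMA-S and the PMDA cohort: "it will be assessed whether site-to-site and geographical heterogeneity exists in the rate of pre-specified primary endpoints". The method is a random-effects meta-analysis, fitted separately for each primary outcome. It has two parts: whether sites differ significantly, and whether geography (US, Canada or Japan) "moderates any statistically significant heterogeneity that is observed". One significance rule is given: "If a Cochran's Q-test for heterogeneity shows $p < 0.05$, it will be taken as evidence of significant heterogeneity between sites". Such a finding prompts further investigation and does not prevent pooling.

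Three other statements in the section bear on the point:

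- The cohorts stay as defined whatever is found: "Heterogeneity analysis findings will not change the composition of the PMA-S and PMDA cohorts".
- Testing is skipped where it would not be meaningful, for example "if < 5 events are observed in all subjects".
- A minimum report is promised, covering comparisons by site and those "between all US, Canadian and Japanese study centers will be shown in the final report in a table by endpoint".

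The section gives up to 25 centers, at most 45 Canadian subjects and a target of 15 Japanese subjects. It does not give the number of sites per country or the scale on which Q is computed.

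**The concern.** Whether sites differ and whether countries differ are separate questions. Q refers to the null that all sites share one rate, and it spreads any country difference over all the between-site degrees of freedom. With 150 to 165 subjects at up to 25 sites, a site contributes about six or seven subjects, so Q has little power against a pattern in which every Canadian site is shifted by the same amount. If the geography moderator is examined only after Q is significant, a country difference that the data could show will usually go untested.

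The PMA-S may draw up to 45 of its 150 subjects (30%) from Canada, and the PMDA submission rests on 15 Japanese subjects combined with the rest. A non-significant Q could be read as showing that the pooled rate applies to each population, when the test was poorly placed to say so.

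**Working it through.** **The plan's own figures.** The exact binomial calculations in SAP 7.1 and 7.2 reproduce. Efficacy: actual alpha 0.0224 and power 0.899 at n = 135; 0.0202 and 0.917 at n = 148. Safety: 0.0141 and 0.860; 0.0233 and 0.932. Neither document states a power for the heterogeneity or geography test.

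**Inputs.** From the SAP: 150 PMA-S subjects, at most 45 Canadian (so at least 105 US), 15 Japanese, up to 25 sites, 54% assumed success, Q tested at 0.05. Assumed: sites of equal size within country; 17 US, 5 Canadian and 3 Japanese sites unless stated; a binary 12-month outcome in place of Kaplan-Meier.

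**Test without the gate, by hand.** Take US 54% (n = 105) and Canada 29% (n = 45).

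- Pooled rate: (105 × 0.54 + 45 × 0.29)/150 = 69.75/150 = 0.465.
- SE under the null: √[0.465 × 0.535 × (1/105 + 1/45)] = 0.0889.
- SE under the alternative: √[0.54 × 0.46/105 + 0.29 × 0.71/45] = 0.0833.
- Power: Φ[(0.25 − 1.96 × 0.0889)/0.0833] = Φ(0.91) ≈ 0.82.

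**Why Q loses it.** The noncentrality of this difference is [105 × (0.54 − 0.465)² + 45 × (0.29 − 0.465)²]/(0.465 × 0.535) = 1.969/0.2488 ≈ 7.9. On 1 df the statistic then averages about 1 + 7.9 = 8.9, against a critical value of 3.84. On 21 df (22 sites) it averages about 21 + 7.9 = 28.9, against a critical value of 32.7. The signal is the same, but on average Q falls short of its threshold.

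**Simulation, no site variation within country** (20,000 trials per row; subject-level chi-square for geography; gated means Q and geography both significant):

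| US vs Canada | No gate | Gated, Pearson Q | Gated, Freeman-Tukey Q | Gated, logit Q |
|---|---|---|---|---|
| 54% vs 44% | 20% | 3% | 5% | 0.1% |
| 54% vs 39% | 39% | 7% | 10% | 0.2% |
| 54% vs 34% | 62% | 14% | 19% | 1% |
| 54% vs 29% | 82% | 25% | 32% | 2% |

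The ordering does not depend on the layout. With 8 US and 3 Canadian sites, the 25-point gap gives 82% against 25% to 41%. With 135 analysed (94 and 41), it gives 79% against 1% to 31%. With Q calibrated to a true 5% level, 15 US and 7 Canadian sites and 46% vs 71%, it is 82% against about 27%.

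**Allowing sites to vary within country.** For 46% vs 71% in the 15 + 7 layout, with geography tested at site level so that between-site variance is respected and Q again held to 5%:

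| Within-site correlation (assumed) | No gate | Gated |
|---|---|---|
| 0 | 79% | 25% |
| 0.05 | 67% | 42% |

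A subject-level test that ignores site rejects a true null of no country difference in about 7%, 8% and 12% of trials at correlations of 0.03, 0.05 and 0.10. The site-level test holds 5%.

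**Japan (15 subjects, 3 sites) against the other 150 at 54%.** Without the gate, chi-square power is about 32% for a 20-point deficit, 47% for 25, 63% for 30 and 79% for 35. Gated, it is 4–7%, 7–12%, 10–18% and 15–26% (Pearson to Freeman-Tukey).

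**Safety.** At the planned 5% rate, 150 subjects give 150 × 0.05 = 7.5 events. For 3% in the US vs 15% in Canada, power is 78% without the gate and 13% gated (Pearson Q), and near zero on the other two scales. For 5% vs 10% it is only about 25% even without the gate.

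**The case against.** The strongest reply is that SAP 6.3 commits without condition to assessing geographical heterogeneity, to fitting a model for each primary outcome, and to a by-country table as a minimum. A reader might infer that geography is examined only through the gate; the text does not support that. It is ambiguous rather than plainly gated. What remains is that the table is promised without a stated estimate, interval or test, and the one geography test described carries the condition. If an unconditional comparison was intended, the section needs the same edit.

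Part of the subgroup section (SAP 6.7) is not visible. Its Kaplan-Meier and log-rank analyses are not tied to Q, so it cannot be said that no other geography analysis exists in the plan. The finding is limited to the visible text.

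A reader might also infer that an ungated test would detect any real difference. It would not: 20% power at 10 points and 39% at 15 even with Canada at its maximum. With 20 Canadian subjects it has 57% at 25 points. For Japan, gaps of 20 to 25 points are missed more often than found.

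Finally, Q exists to detect site variation within country. Where such variation is present the gate opens more often and the loss shrinks, as the second table shows. This point stands. It also argues against a plain log-rank or exact test by country, which would ignore clustering and exceed its nominal 5%.

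**Conclusion.** The concern holds as a matter of wording and power. Followed literally, the condition reduces the chance of finding a 25-point US-Canada difference in success from about 80% to roughly 25% when sites are homogeneous within country, and from about 67% to 42% at a within-site correlation of 0.05. These figures assume Canada at 45 subjects, 22 PMA-S sites of near-equal size and a binary outcome. The SAP does not fix the form of Q, and on the logit scale the gated figure falls to about 2%. A smaller Canadian share lowers power with or without the gate.

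It would be wrong to conclude that the trial's result is at risk. Both primary tests compare pooled rates with fixed goals, and SAP 6.3 says heterogeneity findings alter neither pooling nor cohorts. What is at stake is the reliability of the supporting statement that results are consistent across countries. For Japan, no test on 15 subjects gives much assurance below a gap of about 35 points, so an estimate with its interval is the useful output.

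**What to change.** In SAP 6.3:

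1. Delete the condition. Fit geography as a moderator in the planned random-effects model, allowing for between-site variance, for each primary endpoint whatever Q shows, subject to the existing sparse-event rule. Use US vs Canada in the PMA-S cohort, and add Japan vs the rest in the PMDA cohort.
2. Define the promised table: the 12-month Kaplan-Meier estimate and 95% confidence interval by country for each primary endpoint, with Japan labelled descriptive.
3. Keep Q as a separate description of variation between sites, and state the scale on which it is computed.

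The cost is a few sentences of SAP text and a few lines of code, with no new data. The downside is one or two more exploratory tests per endpoint, which do not affect the type I error of the primary tests.

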17.1. General Considerations

Two analysis cohorts have been defined for this study:

- PMA-S cohort (US/Canada/Europe cohort) – subjects from US, Canada, and Europe centers
- PMDA cohort (US/Canada/Europe/Japan cohort) – subjects from US, Canada, Europe, and Japan centers

Analysis methods are detailed for all objectives in sections 17.1- 17.5. The same methods will be used for both the PMA-S cohort, and also the PMDA cohort. The estimated sample sizes are 150 subjects for the PMA-S cohort, and 165 subjects for the PMDA cohort. The PMDA cohort will have a slight increase in statistical power given 165 subjects will be utilized versus 150.

The Statistical Analysis Plan (SAP) will be created prior to data analysis and include a comprehensive description of the statistical methods to be included in study reports. Any change to the data analysis methods described in the CIP will require an amendment only if it changes a principal feature of the CIP. Any other change to the data analysis methods described in the CIP, and the justification for making the change, will be described in the clinical study report. Medtronic employees or their designated representatives will perform all statistical analyses.

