6.2.2.3. Analysis Methods

The probability of a subject achieving effectiveness success at 12 months (365 days) will be estimated using survival analysis, the Kaplan-Meier method. The standard error will be approximated using Greenwood's formula. A two-sided 95% log-log confidence interval for the probability will be constructed. For every treated subject, day 0 is defined as the day of the index cryoablation procedure. For subjects with treatment failure, the survival date will be set to the date of the treatment failure. For subjects without treatment failure through 12 months, those subjects will be censored at the last study contact date recorded on CRF which may include the last study visit, the exit date, or death date. If a subject without a treatment failure is lost to follow-up, the censoring date will be set to the last known study visit date.

For the component of the endpoint, documented AF/AT/AFL, if this documentation resulted from rhythm monitoring occurring at the 12-month visit within the 12-month visit window, the date of recurrence will be set to 365 days from the study ablation procedure so that these events will be counted as treatment failures in the 12-month Kaplan-Meier analysis. This objective will be analyzed in the mITT dataset: all enrolled subjects who have the Arctic Front Advance Cardiac CryoAblation Catheter inserted into vasculature will be included.

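### The site-heterogeneity test in SAP 6.3 has no controlled 5% level at the planned site sizes, because Cochran's Q is left without an effect scale, a zero-cell rule or a small-sample reference

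*SAP*

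**What the plan says.** SAP 6.3 assesses site and geographic heterogeneity in the primary endpoints "using a random-effects meta-analytic approach", with one model per outcome, for both the PMA-S and PMDA cohorts. The decision rule is that, if Cochran's Q gives p below 0.05, "it will be taken as evidence of significant heterogeneity between sites". Testing is skipped where heterogeneity cannot be assessed meaningfully, "for example, if < 5 events are observed in all subjects". The section does not give the scale on which rates are compared, how sites with no events or only events are handled, or any exact or permutation reference.

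The consequences are limited and stated: "Evidence of between-site heterogeneity will not preclude pooling data". A positive result prompts further investigation, the findings are tabled by endpoint in the final report, and the cohorts stay as defined. Geography is examined as a moderator of any statistically significant heterogeneity that is found.

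On site sizes, the same section expects "up to 25 study centers in the US, Canada, Europe and Japan", and Protocol 17.1 says: "The estimated sample sizes are 150 subjects for the PMA-S cohort, and 165 subjects for the PMDA cohort".

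**The concern.** Q weights each site by the inverse of its estimated variance and refers the sum to a chi-square distribution. That reference is good when each site is large enough to estimate its own variance. With about six subjects per site the variance estimate moves with the rate itself, and a site at 0% or 100% has none without an added constant. The true level then depends on the scale chosen at programming, which the SAP leaves open.

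At stake is what two regulators are told about consistency across sites. The same data could be tabled as homogeneous or as significantly heterogeneous according to an unstated choice. Read literally, the geography question is asked only if the test is significant, so a scale that almost never rejects would also close that step.

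**Working it through.** **Inputs.** Sites: up to 25 (SAP 6.3). Subjects: 150 or 165 (Protocol 17.1), so 150/25 = 6.0 or 165/25 = 6.6 per site at the ceiling. Site cap: 15 in SAP 6.3, 20 in Protocol section 7 (these need reconciling). Success 54% and goal 40% (Protocol 17.3.1); safety events 5% and goal 13% (Protocol 17.3.2).

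**The plan's own figures.** The SAP gives no operating characteristics for Q. Its power tables (SAP 7.1 and 7.2) reproduce by exact binomial:
- Efficacy, N = 135: P(X ≥ 66 | 0.40) = 0.0224 and P(X ≥ 66 | 0.54) = 0.899. N = 148, critical value 72: 0.0202 and 0.917.
- Safety, N = 135: P(X ≤ 9 | 0.13) = 0.0141 and P(X ≤ 9 | 0.05) = 0.860. N = 148, critical value 11: 0.0233 and 0.932.

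**How sparse the sites are.** At six per site:
- P(all or none succeed) = 0.54^6 + 0.46^6 = 0.034.
- P(no safety event) = 0.95^6 = 0.735.
- Expected safety events: 6 × 0.05 = 0.3 per site, 150 × 0.05 = 7.5 in total.
- Expected efficacy failures: 150 × 0.46 = 69, so the five-event guard does not bind for efficacy. For safety, about 88% of trials still pass it.

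**Why the scale matters: one site with 6 of 6 successes.** Q = Σ w_i (y_i − ȳ_w)², with w_i = 1/variance. Take the centre as 54%.
- True variance: 0.54 × 0.46/6 = 0.0414, so the site contributes (1 − 0.54)²/0.0414 = 5.1.
- Raw scale with 0.5 added: rate 6.5/7 = 0.929, variance 0.929 × 0.071/7 = 0.0095, contribution (0.929 − 0.54)²/0.0095 = 15.9.
- Logit with 0.5 added: ln(6.5/0.5) = 2.565, centre ln(0.54/0.46) = 0.160, variance 1/6.5 + 1/0.5 = 2.154, contribution (2.405)²/2.154 = 2.7.

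The raw scale exaggerates an extreme site about threefold (15.9/5.1), and the logit scale roughly halves it (2.7/5.1).

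**Simulated level at nominal 5%, all sites identical, trials with fewer than five events dropped.**

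| Method | 25 × 6, 54% | about 25 uneven sites, 54% | 15 × 10, 54% | 25 × 6, 5% events |
|---|---|---|---|---|
| Q, logit | 0.01% or less | 0% | 0.3–0.6% | about 0% |
| Q, raw | 59% | 35–41% | 31% | about 0% |
| Q, arcsine | 37% | 56–71% | 12% | 1.7% |
| Q, Freeman-Tukey | 8.5% | 6–7% | 5.6% | about 0% |
| Pearson statistic, chi-square reference | 3.8% | not tabled | 4.4% | 4.5% (11% uneven) |
| Pearson statistic, site-label permutation | 4.3% | 5.2% | not run | 2.3% (5.3% uneven) |

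The spread in the uneven column reflects different site-size patterns. Raw-scale results also depend on how zero-variance sites are handled.

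**Detection.** With 25 × 6 and an assumed intraclass correlation (ICC) of 0.05, logit Q rejects 0.3% or less of the time. The permutation test rejects 21% (27% with uneven sites), and 49% (55%) at an ICC of 0.10. At a logit SD of 0.5 with about 25 sites, power is about 20–25%.

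**The case against.** The strongest reply is that the test decides nothing. SAP 6.3 says that pooling continues and the cohorts do not change, and the 40% and 13% decisions never refer to Q. That stands, and it limits the point to a reported result and the steps that follow from it.

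Second, the level depends on choices the SAP has not made, and one of them is tolerable for efficacy: Freeman-Tukey is at 6–9%. That also stands, but Freeman-Tukey almost never rejects for safety, so none of the four inverse-variance scales holds 5% for both endpoints.

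Third, 25 sites is a ceiling across all geographies, and the PMA-S cohort excludes the Japanese centers. Fewer, larger sites would help efficacy: at 15 × 10 Freeman-Tukey is close to nominal. Raw and logit remain far off there, and arcsine gets worse for safety as sites grow, to about 22% at 10 × 15.

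Fourth, the replacement has low power for modest site variation. True, but it does not mistake sparse data for heterogeneity.

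A reader might also infer that the primary interval is too narrow, because "The standard error will be approximated using Greenwood's formula" and no site term enters. The documents do not support that. For these sites taken as fixed, ignoring site does not understate the variance. If sites are viewed as a random sample, the simulated one-sided error at a true 40% is 0.024–0.027 at an ICC of 0.02, 0.034–0.042 at 0.05 and 0.045–0.065 at 0.10. The documents give no ICC from which to choose.

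**Conclusion.** The point holds as one of specification and calibration. With 150–165 subjects over about 25 sites, the stated rule has a true level of about 0% (logit), 33–59% (raw), 37–56% (arcsine, higher in some very uneven layouts) and 6–9% (Freeman-Tukey) at 54% success, and about 0–3% on all four at a 5% safety rate. The figures assume identical true site rates, binary 12-month outcomes without censoring, and site layouts that the documents do not fix. For efficacy the distortion shrinks with fewer, larger sites but persists on the raw and logit scales at 15 × 10.

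What is affected is the heterogeneity result in both submissions, the trigger for further investigation and the geography-moderator step. The trial's 0.025 alpha, the pooling and the cohorts are not. Part of the SAP between 6.5 and the subgroup text is not visible, so a related analysis there cannot be ruled out. The importance is low and the remedy is cheap.

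**What to change.** In SAP 6.3, replace the chi-square p-value with a site-label permutation (Monte Carlo exact) p-value for each primary endpoint. Use either a Pearson statistic on 12-month status, with a stated rule for subjects who leave early, or a log-rank statistic across sites. The log-rank form treats censored subjects as the Kaplan-Meier primary analysis does, and assumes that follow-up patterns do not differ by site. Report the estimated between-site SD with its interval, so that a non-significant result is not read as proof of homogeneity. Assess and report geography whatever the site test shows. If Q is kept as a descriptive statistic, name its scale and zero-cell rule.

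A sensitivity interval from resampling whole sites is optional. It matters only if sites are viewed as a random sample with an ICC well above 0.02.

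The cost is SAP wording and a little more programming. Cohorts, primary analyses and sample size do not change. Power for modest site variation stays low, at about 20–25% for a logit SD of 0.5 with about 25 sites, and the report should say so.
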